cardiac death⁴⁵⁻⁴⁹. Fractal analysis of metabolomic data will allow us to test whether the Hurst exponent is related to clinical outcomes and/or response to nutritional interventions in the ICU patients we propose to study.

Emerging data strongly suggest that microbes of the intestine (the microbiota) play a key role in host metabolism, immune/inflammatory processes and disease pathophysiology⁵⁰⁻⁵². The intestinal microbiome (genome of the gut microbiota) is shaped by both environment (e.g. diet) and host genetics; and, vice versa, the gut microbiota itself appears to regulate a wide spectrum of host immune, inflammatory and metabolic responses⁵³. **Human data on the impact of nutrition support during critical illness on the gut microbiome are limited.**

Despite limited evidence, there is a suspected interplay between critical illness and the gut microbiome, which warrants further exploration in the setting of nutrition support⁵⁴⁻⁵⁸. Nelson et al utilized 16S rRNA pyrosequencing to characterize stool of hospitalized patients and observed perturbations in gut microbiota following infection⁵⁹. It is acknowledged that the microbiome plays an integral role in health maintenance, and that modifications of the gut microorganisms may influence outcomes in critically ill patients.

Hypothesis:

- 1) Adequate energy administration (defined as 1.3 x REE) will result in a lower 28-day total hospital-acquired infection rate compared with ICU patients receiving lower energy doses.
- 2) Differences in energy intake will result in global changes in metabolic patterns that themselves are associated with clinical outcomes in the ICU patients studied.

Specific Aims:

- 1) To perform a controlled, double-blind, prospective, randomized, parallel group, intent-to-treat Phase II clinical trial to test the efficacy of three specific energy doses [0.6, 1.0 and 1.3 x measured REE (metabolic cart), respectively], given for 28 consecutive days during the ICU course, on 28-day total hospital-acquired infections (primary endpoint), BSI, and other important clinical outcomes in medical/surgical ICU patients requiring specialized parenteral ± enteral feeding.
- 2) In Aim 1 subjects to: a) examine the impact of cumulative and mean daily 28-day energy deficits [energy intake-measured REE] on clinical outcome endpoints; and b) to estimate the agreement for REE as determined by the HBE and the measured REE across different energy doses.

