Study Schema: Controlled, randomized, double-blind, prospective, parallel-group, intent-to-treat **Aim 1** clinical trial to test the efficacy of three energy doses [0.6, 1.0, and 1.3 x measured REE (MREE), by metabolic cart, respectively], given for 28 consecutive days during the ICU and post-ICU course in critically ill medical and surgical patients requiring parenteral nutrition (PN) ±enteral nutrition (EN) at Emory University. The primary endpoint is total hospital-acquired infections after entry; secondary endpoints are bloodstream infections, ventilator-free days, and ICU and 28-day hospital length of stay and mortality. **Aim 2** examines the effect of cumulative and mean daily measured 28-day energy deficits after entry on Aim 1 clinical outcome endpoints and relationships between estimated REE (Harris-Benedict equation) at study entry. **Aim 3** explores the impact of energy dose and cumulative and mean daily 28-day energy deficits on global metabolomic patterns, microbiome, and strength over time and in association with key clinical outcomes in Aim 1.

↑ Plasma (metabolome), microbiome, and strength analysis

Data Collection: Baseline data collected will include APACHE II score, and clinical and demographic data. The following will be collected during the course of the study:

A) Measured resting energy expenditure (MREE; per metabolic cart) will be determined on the baseline day before 2 pm. The goal energy dose composition of PN for all three energy doses for each enrolled subject is calculated by the blinded research team members. The metabolic cart-derived REE will be used to determine basal energy expenditure (REE) and thus the initial energy dosing^{5, 10, 12}. MREE will be determined at baseline and 5x weekly (M-F before 2 pm; see Aim 2) using a state-of-the-art metabolic

cart and standard methodologies by a study team respiratory technician with prior experience and expertise in clinical indirect calorimetry. In the event that the metabolic cart is not available, the most recent measurements will be used. The nutrition will not be adjusted if the MREE is <10% changed from the reading the day before.

- B) Longitudinal SOFA scores of organ dysfunction/failure: Sequential organ failure assessment (SOFA) scores will be calculated in the morning of each ICU day ⁶⁰. The baseline Apache II score on the day of ICU admission will also be calculated in all patients.

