Determination of energy deficit: Energy intake from PN \pm EN (tube feeds + any oral diet) will be determined as outlined in Aim 1 each day for the initial 28-days of study. MREE will be determined by metabolic cart 5x week (Monday through Friday) before 2 pm. Any PN or EN being administered will be continued uninterrupted during MREE determinations. The 5 daily cart measurement results (kcal/day) for each study week will be averaged and that mean daily value used as the daily measured energy requirement for all 7 days of that week. The daily energy deficit will be calculated by subtracting the calculated mean daily MREE during each study week from the actual daily energy intake. The cumulative and mean daily ICU and 28-day energy deficits will be determined. Metabolic cart measurements will not be performed on any given day in patients whom are in isolation due to resistant microorganism infection (contraindicated), or if the patient requires a fraction of inspired oxygen of < 60%, has a requirement for positive end-expiratory pressure of > 12 cm H₂O, or has a documented leak in the ventilator or chest tube systems (precluding accurate cart measurements) ^{32, 33}. The estimated REE by the HBE(outlined in detail in Table 3 of reference 3 ⁶¹) will be calculated on the baseline day using most recent available pre-ICU dry body weight.

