Data and Safety Monitoring Board (DSMB): The Data and Safety Monitoring Board (DSMB) will act in an advisory capacity to the National Institute of Diabetes, Digestive and Kidney Diseases (NIDDK) to monitor subject safety and evaluate the efficacy of the intervention being studied in this clinical trial funded by the NIDDK. The DSMB will be appointed by the PIs upon study funding, and approved by NIDDK program staff. The DSMB will be composed of at least two experienced clinical nutrition support investigators not otherwise participating in the study and not affiliated with Emory. A biostatistician not otherwise participating in the study will also be named to the DSMB. The DSMB will meet twice yearly, and as needed, and will receive blinded and unblinded reports on study progress prepared by the DCC.

Statistical Analysis:

Continuous variables will be summarized with standard descriptive statistics and represented graphically with displays such as scatterplots, box plots, line plots and histograms, while categorical variables (adverse events) will be described by frequency tables.

For Aim 1: The primary analyses of the data will be performed according to subjects' original treatment assignment (i.e., intention-to-treat analyses) and the inclusion of all data from all subjects randomized in the final analysis. Rates of infection (i.e., BSI and total nosocomial infections) per 1000 hospital days will be estimated overall and for each of the 3 energy doses. Confidence intervals (95%) for the incidence rates will be estimated using an exact method based on the Poisson distribution.

Additionally incidence rates of infection will be estimated by performing a generalized estimating equations (GEE) Poisson regression analysis of the counts, implemented using SAS Proc Genmod, using an exchangeable correlation structure for the repeated counts within subject. The incidence rate ratio (IRR) is the ratio of the incidence density in one group to that of another group. Results by each baseline covariate will be presented as the IRR and the 95% confidence interval (CI). This GEE model can also accommodate time-dependent covariates such as daily blood glucose levels measured before an infection and total 28-day energy (cumulative deficit or as a time-dependent covariate).

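### Aim 2a sets no time order between energy deficit and infection, and its cumulative 28-day deficit scales with length of stay

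*Combined protocol and SAP*

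**What the plan says.** Specific Aims (Aim 2a) sets out to "examine the impact of cumulative and mean daily 28-day energy deficits [energy intake-measured REE] on clinical outcome endpoints". The Study Schema repeats that Aim 2 "examines the effect of cumulative and mean daily measured 28-day energy deficits after entry on Aim 1 clinical outcome endpoints". The section on determination of energy deficit subtracts a weekly mean of cart readings from each day's intake, with "that mean daily value used as the daily measured energy requirement for all 7 days of that week". It then states: "The cumulative and mean daily ICU and 28-day energy deficits will be determined".

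The Statistical Analysis text headed For Aim 2 contains no deficit-outcome model. It covers only agreement between the Harris-Benedict equation (HBE) and measured resting energy expenditure (REE), and an ANCOVA. The one place where deficit meets an outcome is under For Aim 1, in the infection model, a Poisson GEE "using an exchangeable correlation structure for the repeated counts within subject". There the plan says: "This GEE model can also accommodate time-dependent covariates such as daily blood glucose levels measured before an infection", and adds "total 28-day energy (cumulative deficit or as a time-dependent covariate". The time restriction belongs to glucose. None is given for energy.

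For Aim 2b the ANCOVA asks whether the administered caloric dose changes the relationship between serial REE and entry HBE. It gives neither the unit of dose nor the coefficient to be tested.

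**The concern.** A deficit measured over the whole 28 days includes days on and after the infection it is meant to explain. If infection leads to less feeding, a null relationship looks like harm from underfeeding. A same-day deficit has the same weakness if feeding drops on the day of diagnosis.

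The cumulative total has a second problem that needs no reverse causation. It is a daily balance multiplied by days observed, so length of stay is built into it.

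Aim 2 is meant to help design a Phase III trial, and the Background criticises earlier observational evidence on energy balance. An ambiguous association here would repeat that weakness.

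**Working it through.** **Inputs.** From the documents: 60 patients, 20 per arm, at 0.6, 1.0 and 1.3 x REE; deficit = daily intake minus weekly mean measured REE. The documents give no infection rate, delivery percentage, length of stay or effect of infection on intake, and no power or precision figure for Aim 2 to reproduce. All other inputs are assumed.

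**1. Cumulative balance and days observed.** For multiple k, delivered fraction f and D days, cumulative balance = (k x f - 1) x REE x D. With REE assumed at 1,800 kcal/day and f = 1:

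| Multiple | Daily | 7 days | 14 days | 28 days |
|---|---|---|---|---|
| 0.6 | -720 | -5,040 | -10,080 | -20,160 |
| 1.0 | 0 | 0 | 0 | 0 |
| 1.3 | +540 | +3,780 | +7,560 | +15,120 |

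The total moves with stay even at full delivery, in opposite directions in the outer arms. In a null simulation at full delivery, its mean within-arm correlations with stay were -0.82 (0.6 x) and +0.60 (1.3 x). The 1.3 x arm stays in surplus until f falls below 1/1.3 = 0.77.

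Pooled over equal arms, the mean daily balance is ((0.6 + 1.0 + 1.3)/3 x f - 1) x REE. This is -0.033 REE at f = 1, -0.082 at 0.95, -0.178 at 0.85 and -0.275 at 0.75. The arms nearly cancel at full delivery and stop cancelling as delivery falls.

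**2. False positives for length of stay.** The plan names no model, so this is an assumed linear regression with HC3 standard errors, 60 patients, and stay generated independently of deficit. Unadjusted / arm-adjusted rejection at nominal 5%:

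| Steady delivery | Cumulative total |
|---|---|
| 75% | 78-97 / 96-100% |
| 85% | 37-56 / 68-96% |
| 95% | 9-12 / 14-25% |
| 100% | 4-5% |

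The mean daily deficit gives 4-6% under steady delivery. If delivery changes over the stay it also fails: 5-29 / 4-84% when study PN stops as the protocol provides and intake then runs at 50-90% of REE, and 13-15 / 38-91% after a slow start on days 1-3. A days 1-7 window gives 3-11%. For death, the cumulative total gives 1-21 / 2-26% and the mean 3-5 / 3-17%. For ventilator-free days the figures are 4-11 / 4-19% and 3-7 / 3-12%.

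**3. Why a fall in intake matters for infection.** Take a 1.0 x patient at 90% delivery with a 20-day stay and a 20% fall for 7 days. The mean balance shifts by 0.2 x 0.9 x 7/20 = 0.063 REE, or 113 kcal/day at 1,800. A between-patient delivery SD of 5-12 points is 90-216 kcal/day, so within an arm the shift is visible. Arm gaps at 90% delivery are 0.4 x 0.9 x 1,800 = 648 and 0.3 x 0.9 x 1,800 = 486 kcal/day, which dilute it when arm is left out.

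**4. False positives for infection.** Assumed grid: 2-6% per day, delivery 75-90%, fall lasting 3-14 days, delivery SD 5-12 points; 36 settings, 300 null trials each per fall size; Poisson with Mancl-DeRouen standard errors. Unadjusted / arm-adjusted, with the arm-adjusted median in brackets:

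| Fall | Whole-period mean | Cumulative | Same day, no lag |
|---|---|---|---|
| None | 3-6 / 2-6% (4) | 4-6 / 4-7% (5) | (6) |
| 10% | 4-11 / 5-56% (17) | 4-9 / 5-21% (10) | 16-57 / 36-99% (66) |
| 20% | 4-26 / 10-94% (53) | 5-21 / 7-56% (24) | 56-100 / 92-100% at 20-30% (100) |
| 30% | 8-59 / 16-100% (81) | 8-44 / 10-79% (42) | as above (100) |

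A one-day lag gives 4-7 / 2-6%, with a median of 4% whether or not the weekly mean REE is kept. In the plan's own form (person-day GEE, exchangeable, arm-adjusted) at falls of 0, 20 and 30%, the whole-period mean gives 5.7, 57.3 and 86.7% and the one-day lag 7.3, 8.3 and 7.7%. The lagged figure is slightly above nominal but does not rise with the fall. A second simulation, arm-adjusted at a 20-30% fall, gave 34-98% for whole-period deficits, 100% for same-day and 4-8% for the mean through the day before.

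If a 20-30% fall starts two days before diagnosis, the one-day lag gives 11-57 / 24-100% and a three-day lag 3-6 / 0-6%.

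**5. Aim 2b in the ICU.** With dose set from measured REE, a kcal main effect rejects in 19-99% of null trials, because kcal is built from the response. The HBE x kcal interaction rejects in 3-6%, and HBE x arm in 5-7%.

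**The case against.** The strongest reply is that the infection harm is conditional. No section says that intake falls after infection, and the nutrition-support section aims to hold intake at its daily goal. The GEE sentence describes what the model can take rather than a committed test, and it does not say that arm and deficit share a model, which is where the largest figures arise. All of this stands: with no fall there is no material inflation, and a 10% rise in REE with no fall in intake gives only 5-7%. What remains is that a restriction stated for glucose is missing for energy.

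The mean daily deficit is already planned, which is also true. It removes the built-in link with stay when delivery is steady, but it does not restore time order for infection.

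Several stronger readings are tempting:
- A reader might infer that the cumulative total grows with stay only when delivery is below goal. The arithmetic shows otherwise.
- The error rates for stay, death and ventilator-free days might be taken as the plan's own. They belong to an assumed regression, because the plan names none.
- Weekly averaging of REE does let later readings into earlier days, but its effect alone is negligible.
- Aim 2b might be called circular. Its question, whether dose changes the agreement of HBE with "the measured REE across different energy doses", reads naturally as an interaction, and that term stays near nominal. Substituting randomised arm for administered dose would change the question.

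**Conclusion.** The point holds in limited form and should be settled before analysis. Two faults are supported by the text: energy deficit has no time order relative to infection, and the cumulative total carries length of stay within it.

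The size of the first depends on an assumed fall in intake: negligible without one, and with arm in the model a median of 53-81% false positives for the whole-period mean at a 20-30% fall. The second needs no fall. Pooled over arms it is nominal at full delivery and strong at 75-85% delivery, under an assumed model. The absence of any stated model for deficit against stay, death or ventilator-free days is itself a gap.

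The documents do not support saying that Aim 2a will yield false findings, that the Aim 2b ANCOVA is invalid, or that the randomised comparison is compromised. The aim is secondary in a pilot, and the intention-to-treat analysis is untouched.

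A separate contradiction remains. Potential Risks describes the doses as multiples of HBE-estimated REE, while Specific Aims, Study Schema and the nutrition-support section use measured REE.

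**What to change.** 1. **Infections (For Aim 1, GEE covariates).** Use the mean daily deficit through the day before as the time-dependent covariate, in a model separate from the intention-to-treat comparison. Repeat with a longer lag, such as three days, because a one-day lag fails if intake falls before diagnosis. Replacing the weekly mean REE with the latest available reading is optional.
2. **Length of stay, death, ventilator-free days.** State a model. Do not use the cumulative 28-day total. Use the mean daily deficit already defined, labelled associational. Plan a sensitivity analysis with a fixed early window, such as days 1-7 with outcomes counted afterwards, because the mean is distorted when delivery changes over the stay.
3. **For Aim 2 (minor).** State the dose scale, name HBE x dose as the tested term, and do not interpret a kcal main effect in the ICU. HBE x randomised arm may be added in support.
4. **Potential Risks.** Reconcile the description of the dose base with the other sections.

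The cost is wording only; intake is already recorded daily. Lagging loses the first day or days of follow-up. The early window drops early deaths and discharges, 5-15% of patients under the assumed stays. HBE x arm is imprecise at 20 per arm: the 95% CI half-width for a slope difference is about 0.23-0.95 if the residual REE SD is 5-20%.

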Comparative effectiveness of energy doses in critical illness

Short title: The Energy Dose Study

Principal Investigator: [name].

Protocol Version Date: 6/2/2014

NCT Number: NCT01369147

Abstract:

Protein and/or energy deficits are associated with increased rates of hospital infection, skeletal muscle weakness, impaired wound healing, and prolonged convalescence in ICU patients. To prevent or treat malnutrition, enteral nutrition (EN) and/or parenteral nutrition (PN) are routinely given worldwide to a significant proportion of ICU patients. Optimal caloric requirements in critically ill patients are unknown due to a lack of rigorous randomized clinical trials. The comparative efficacy of energy doses in critically ill patients is unknown and clinical recommendations are conflicting and controversial; this issue is the focus of our study.

We have designed this pilot, single-center Randomized Clinical Trial (RCT) to prospectively compare, for the first time, the clinical efficacy of different energy doses in ICU patients requiring PN due to intestinal failure/dysfunction. A total of 60 patients will be studied (20 per energy dose group) to generate critical preliminary data needed to inform subsequent appropriately powered Phase III multicenter trials.

The primary aim of this study is to perform a controlled, double-blind, prospective, randomized, intent-to-treat Phase II clinical trial to test the efficacy of three specific energy doses [0.6, 1.0 and 1.3 x measured REE (resting energy expenditure), respectively], given for 28 consecutive days during the ICU course, on 28-day total hospital-acquired infections (primary endpoint), Blood Stream Infections (BSI), and other important clinical outcomes in medical/surgical ICU patients requiring specialized parenteral \pm enteral feeding. We would also determine, in these subjects A) the impact of cumulative and mean daily 28-day energy deficits [energy intake-measured REE] on clinical outcome endpoints; and B) the practical utility of estimated REE determined by Harris-Benedict equation versus measured REE across different energy doses. We would also like to determine the impact of administered energy dose and energy deficits on global metabolomic patterns over time and their association with key clinical outcomes.

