Exclusion criteria: 1) The patient is pregnant; 2) The patient has unresuscitated clinical sepsis [defined as unstable blood pressure despite vasopressor support and mean arterial pressure (MAP) < 60 mm Hg on at least 3 consecutive readings within a 3-hour period during the 24 hours prior to study entry; 3); 3) The patient was admitted to the ICU following trauma or burns; 4) The patient has significant renal dysfunction (defined as serum creatinine > 2.5 mg/dL or deemed to have significant acute kidney injury by the primary physicians) and is not receiving continuous renal replacement therapy (CRRT) or intermittent hemodialysis; 5) The patient has previously undergone an organ transplantation; 6) the patient has a current malignancy or is currently receiving an active regimen of chemotherapy and/or radiotherapy to treat a previously diagnosed malignancy[#]; 7) the patient has a history of HIV/AIDS; 8) The patient has received any investigational drug within 60 days prior to study entry; and 9) The patient is unable or unwilling to participate in study procedures such as longitudinal blood draws and administration of study nutrient formulations.

[#] [†] Patients with malignant metastasis and terminal untreatable carcinoma will be excluded.

If the patient meets criteria, we will consent the patient's legally authorized representative (LAR), as potential study subjects will be mechanically ventilated and probably sedated.

Randomization of study subjects: A research team member will calculate the APACHE II score. Treatment assignments will be stratified according to clinical center and on the basis of illness severity (APACHE II score, either ≤ 15 or > 15). The treatment assignments will be generated by the Emory-based DCC with the use of a pseudo-random-number generator with randomly permuted blocks that will be used to ensure balance between the numbers of subjects assigned to the REE x 0.6, 1.0 or 1.3 groups, respectively.

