Twenty-eight day mortality will be summarized as a proportion plus the 95% confidence interval (overall and for each treatment group). The 28-day mortality will be compared between treatment groups using a chi-square or Fisher's exact test. The potential association of each of the categorical prognostic factors (gender, race, high or low Apache score, clinical center) with mortality will also be evaluated using a Chi-square test or Fisher's exact test. Baseline continuous prognostic factors (age, SOFA score, blood glucose) will be compared by treatment group using the Wilcoxon rank-sum test. Odds ratios will be calculated to measure the degree of association. All statistical tests will be 2-sided. Factors significant to at least a value of $P \leq 0.20$ in the univariable analyses will be used in multivariable logistic regression analyses. Forward and backward stepwise selection will be used if necessary to choose prognostic variables for a multivariable logistic regression model. The odds ratio and its 95% confidence interval will be calculated for each factor in the presence of others in the final model.

Days on mechanical ventilation, length of ICU stay and hospital length of stay will be summarized with percentiles (25th, 50th and 75th) and the median absolute deviation. These secondary outcomes will be compared between the 3 treatment groups using the Kruskal-Wallis test. Repeated-measures analyses of daily SOFA scores and laboratory measures such as blood glucose will be analyzed with a means model with SAS Proc Mixed (version 9, mixed linear models) providing separate estimates of the means by time on study (days 0, 3, 7, 14, 21, and 28) and treatment group (energy dose: 0.6, 1.0 and 1.3 x REE). An unstructured variance-covariance form among the repeated measurements will be assumed for each outcome and estimates of the standard errors of parameters will be used to perform statistical tests and construct 95% confidence intervals. T-tests will be used to compare the pairwise differences between the model-based treatment means (least-squares means) at each time point. Statistical tests will be 2-sided. The model-based means are unbiased with unbalanced and missing data, so long as the missing data are non-informative (missing at random). A dropout process is assumed to be missing at random if; conditional on the observed data, the dropout is independent of the unobserved measurements.

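### APACHE II enters the 28-day mortality prognostic analysis only as high or low although the numeric score is calculated for every patient; under stated assumptions this loses about 36% to 51% of the information on its association with death

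*Combined protocol and SAP*

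**What the plan says.** The score is available for everyone. Under Randomization of study subjects, "A research team member will calculate the APACHE II score", and treatment assignment is stratified by clinical center and by "illness severity (APACHE II score, either ≤ 15 or > 15". Data Collection, item B, adds: "The baseline Apache II score on the day of ICU admission will also be calculated in all patients".

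The mortality plan is in Statistical Analysis, For Aim 1, and has four parts:

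- Treatment comparison: "The 28-day mortality will be compared between treatment groups using a chi-square" or Fisher's exact test, with no covariates.
- Categorical prognostic factors: the association of "each of the categorical prognostic factors (gender, race, high or low Apache score, clinical center) with mortality will also be evaluated" by the same kind of test.
- Continuous factors: "Baseline continuous prognostic factors (age, SOFA score, blood glucose) will be compared by treatment group using the Wilcoxon rank-sum test". APACHE II is not on this list.
- Multivariable step: factors reaching P ≤ 0.20 "in the univariable analyses will be used in multivariable logistic regression analyses", with stepwise selection if needed and an odds ratio for each factor in the final model.

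The mortality paragraph does not restate the cut for high or low. That it is 15 is an inference, but no other cut appears in the documents. Nowhere is the numeric APACHE II score modelled against death.

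**The concern.** APACHE II is the severity measure on which the investigators chose to stratify. Reducing it to two levels treats scores of 16 and 35 as the same and 15 and 16 as different. SOFA, the other severity score, is classed as continuous, and no reason is given for handling the two differently.

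Two consequences follow within the prognostic analysis. First, the univariable test of APACHE II against death is weaker than it need be, so the factor is more likely to miss the P ≤ 0.20 threshold and drop out. Second, if it drops out or enters as two levels, the model adjusts incompletely for severity, and the odds ratios of the other factors carry what is left over. The trial is a pilot meant to inform later multicenter trials, for which an odds ratio per few points is more useful than a contrast of high with low.

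**Working it through.** The plan states no power, event count or score distribution for mortality, so it has no figure to reproduce.

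**Inputs from the documents.** Sample size: "A total of 60 patients will be studied (20 per energy dose group" (Abstract). Cut at 15 (Randomization of study subjects). Two-level use, 2-sided tests and the P ≤ 0.20 screen (Statistical Analysis, Aim 1).

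**Assumed inputs.** The share p of patients above 15, the shape of the score, log-odds of death linear in the score, and mortality of 10% to 30%. That mortality gives 60 × 0.10 = 6, 60 × 0.20 = 12 or 60 × 0.30 = 18 deaths.

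**Step 1: information kept by the split.** For a normal score and a small effect, the large-sample efficiency of the two-level version relative to the numeric score is φ(z)² / [p(1 − p)], where z is the normal quantile for p and φ is the normal density.

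| Share above cut | φ(z) | φ(z)² | p(1 − p) | Kept | Lost |
|---|---|---|---|---|---|
| 50% | 0.3989 | 0.1592 | 0.25 | 0.637 | 36% |
| 70% | 0.3477 | 0.1209 | 0.21 | 0.576 | 42% |
| 80% | 0.2800 | 0.0784 | 0.16 | 0.490 | 51% |
| 90% | 0.1755 | 0.0308 | 0.09 | 0.342 | 66% |

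The formula is symmetric in p, so 20% above the cut gives the same result as 80%. The range for 20% to 80% is therefore 36% to 51%.

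**Step 2: sensitivity to mean and shape.** With a normal score and SD of 6 to 8, assumed means of 12 to 20 give losses of 36% to 48%, a mean of 22 gives 50% to 59%, and a mean of 25 gives 63% to 76%. For other shapes the loss was taken as one minus the squared correlation between score and indicator. With 20% to 80% above the cut it is 25% to 52% for a uniform score, about 36% to 69% for right-skewed scores (gamma, lognormal), and 46% to 55% for a heavy-tailed score.

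**Step 3: effect on the P ≤ 0.20 screen.** A simulation with N = 60 and 1,500 runs per scenario compared a rank-sum test of the numeric score with Fisher's exact test of the split. Simulation error is at most √(0.25/1500) = 0.013. The table gives the chance of passing the screen at an assumed odds ratio of 2 per SD.

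| Assumed mortality | Numeric score | Split, 50% above | Split, 70% above | Split, 80% above |
|---|---|---|---|---|
| 10% | 0.58–0.59 | 0.36 | 0.24 | 0.11 |
| 20% | 0.75–0.76 | 0.58 | 0.45 | 0.35 |
| 30% | 0.83–0.84 | 0.65 | 0.58 | 0.48 |

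The direction is the same at odds ratios of 1.5 and 2.5. At 20% mortality the first gives 0.45–0.47 for the numeric score against 0.31, 0.25 and 0.22 for the split. The second gives 0.88–0.89 against 0.70, 0.61 and 0.45. Part of each gap reflects the conservatism of Fisher's test in small tables, not the split alone. The plan allows chi-square or Fisher.

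**The case against.** The strongest case for leaving the plan alone is that high or low is the randomisation stratum, so using it in the analysis is consistent with the design. This is also a pilot, mortality is a secondary endpoint, and linear coding is itself an assumption. All of that is true. But stratifying at a cut does not require analysing at it. A linear term uses one degree of freedom, the same as the split, and the stratum indicator can stay in the model beside the numeric score if wanted.

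Four stronger readings are tempting, and the documents do not support them.

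- A reader might infer that the split weakens or biases the comparison of mortality between energy doses. That comparison is an unadjusted test in which APACHE II does not appear. The logistic model is described as selecting prognostic variables, and the plan does not say that treatment is in it.
- A reader might take a loss of a third to a half as a property of this trial. The documents give no mean, SD, shape or share above 15. Step 2 shows losses from about 25% to above 70%.
- Since 60 × 0.637 = 38 and 60 × 0.490 = 29, a reader might say that the trial shrinks to 38 or 29 patients. Those equivalents apply only to the one association between APACHE II and death.
- A reader might take it as stated that deaths will be few. No rate is given, and the Adverse Event section says mortality in such patients is high. A small count, 6 to 18, follows only from N = 60 and an assumed 10% to 30%.

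**Conclusion.** The point holds as a limited improvement to a secondary prognostic analysis. The plan uses APACHE II against 28-day death only in two levels when the numeric score is on hand for every patient. Given a near-normal score, log-odds linear in it, and 20% to 80% of patients above the cut, about 36% to 51% of the information in that association is lost. A more uneven split loses more. The practical effect is a lower chance that the trial's own severity measure survives the P ≤ 0.20 screen, and less complete severity adjustment of the other factors' odds ratios. The primary infection endpoint and the treatment comparison of mortality are unaffected, so this is desirable rather than necessary.

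**What to change.** In the mortality paragraph of Statistical Analysis, For Aim 1:

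1. Remove APACHE II from the categorical factors.
2. Test the numeric score against 28-day death by univariable logistic regression, or by a rank-sum test of survivors against non-survivors.
3. Enter it as a linear term in the multivariable logistic model, state whether that entry depends on the P ≤ 0.20 screen, and report the odds ratio with its 95% confidence interval per 5 points.
4. Keep the cut at 15 as the randomisation stratum.

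Simply adding APACHE II to the existing list of continuous factors would not do. Those factors are compared between treatment groups, not between patients who died and those who survived, so the move would remove the only univariable mortality test APACHE II now has. For the same reason the plan states no univariable mortality test for age, SOFA or glucose; the new sentence could cover them too.

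The cost is a sentence or two of wording. The score is already collected.
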